4.2 CONCOMITANT THERAPY, RESTRICTIONS, AND RESCUE TREATMENT

4.2.1 Rescue medication, emergency procedures, and additional treatment(s)

Concomitant therapies should be limited to those essential for the non-gastrointestinal care of the patient. All concomitant medications and the reason(s) for use will be documented throughout the course of the study.

In case of infusion reactions emerging during or after infusion of BI 655066/ABBV-066 (risankizumab), the investigator should consider in accordance with severity of the reaction and local standard of care to

- immediately interrupt the infusion
- treat with systemic anti-histamines and intravenous steroids

Based on patient's clinical course and medical judgment, the infusion may be re-initiated in case of mild or moderate reactions (according to RCTC grading in [Appendix 10.3](#)) at

lower speed with gradual increase to complete the infusion as detailed in the Instructions for Preparation and Handling of BI 655066/ABBV-066 (risankizumab) in the Investigator Site File.

In case of adverse events in need of treatment, symptomatic therapy according to the judgment of the investigator will be permitted. All concomitant and/or rescue therapies will be recorded on the appropriate pages of the eCRF.

There are no special emergency procedures to be followed.

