4.2.2.1 Restrictions regarding concomitant treatment (cont.)

Medications	Restriction time period
Systemic corticosteroids (eg, prednisone, budesonide)	
 Parenteral (SC, IM, or IV) or rectal corticosteroids are not permitted during the study and must not have been used within a 4-week period prior to visit 2. Oral corticosteroids must be at a prednisone-equivalent dose of ≤ 20 mg/day, or ≤ 6 mg/day of budesonide, and have been at a stable dose for at least 4 weeks prior to visit 2. If oral corticosteroids were recently discontinued, discontinuation must have been completed at least 3 weeks prior to visit 2.

Crohn's disease-specific antibiotics	If using a Crohn's disease-specific antibiotic for treatment of Crohn's disease, patients must have been using the antibiotic for at least 4 weeks before visit 2 at a stable dose. If not currently using a Crohn's disease-specific antibiotic, the stop date must have been at least 4 weeks prior to visit 2.
Opioids	Patients with regular daily opioid use over the past 3 months before screening are excluded due to the interference of such medication with key efficacy endpoints (CDAI)
Live or attenuated vaccines (during study or 140 days after last dose of study drug)	
• live attenuated influenza (intranasal)• herpes zoster• rotavirus• varicella (chicken pox)• measles-mumps-rubella (MMR) or measles mumps rubella varicella (MMRV)• oral polio vaccine (OPV)• smallpox• yellow fever• Bacille Calmette-Guérin (BCG)• oral typhoid

Tapering of corticosteroids

The tapering of prednisone dosage or equivalent (see [Appendix 10.2](#)) of other systemic corticosteroids is requested for patients achieving clinical remission the first time while on treatment with BI 655066. In such patients steroids must be tapered at a maximum rate of 2.5 mg per week to a dosage of 0. If a patient experiences a loss of clinical response (decrease in CDAI < 100 points from baseline on 2 consecutive visits) during steroid tapering, the dosage of prednisone may be increased back to the dosage used at study entry.

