RSI in place at the time of occurrence of the 'suspected' Serious Adverse Reaction will be used to assess expectedness.

Information required

The following should also be recorded as an (S)AE in the (e)CRF and SAE form (if applicable):

- Worsening of the underlying disease or of other pre-existing conditions
- Changes in vital signs, ECG, physical examination and laboratory test results, if they are judged clinically relevant by the investigator

If such abnormalities already pre-exist prior trial inclusion they will be considered as baseline conditions.

All (S)AEs, including those persisting after individual patient's end of trial must be followed to a satisfactory conclusion or no further information can be obtained.

Pregnancy

Pregnancy in a study subject must be reported to AbbVie within 1 working day of the site becoming aware of the pregnancy. Subjects who become pregnant during the study must be discontinued from study drug.

Information regarding a pregnancy occurrence in a study subject and the outcome of the pregnancy will be collected.

Pregnancy in a study subject is not considered an AE. However, the medical outcome of an elective or spontaneous abortion, stillbirth, or congenital anomaly is considered an SAE and must be reported to AbbVie within 24 hours of the site becoming aware of the event.

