4.3.2 Secondary Efficacy Endpoint

- Clinical remission by visit defined as a CDAI < 150.
- Clinical response by visit, defined by either a CDAI < 150 or a CDAI reduction from baseline of at least 100 points.
- PRO-2 remission by visit, defined by a PRO-2 score < 75
- PRO-2 response by visit, defined as a decrease from baseline of 50 points or more.
- CDEIS remission, defined as a score of 4 or less, by visit (for patients with initial isolated ileitis a score of 2 or less)
- CDEIS response, defined as a score of 7 or less, by visit (for patients with initial isolated ileitis > 50% reduction from baseline).

- Mucosal healing, using CDEIS defined as the absence of mucosal ulceration, i.e., ulceration sub-score (deep ulceration, superficial ulceration, ulcerated stenosis) is 0, by visit.
- Deep remission, defined as clinical remission and CDEIS remission by visit.
- IBDQ remission (IBDQ total score > 170 points) by visit.
- IBDQ response (increase in IBDQ total score > 16 points from baseline) by visit.
- Change from baseline in CDAI by visit.
- Change from baseline in PRO-2 scores by visit.
- Change from baseline in CDEIS by visit.
- Change from baseline in SES-CD by visit.
- Change from baseline in stool frequency (SF) by visit based on patient diary.
- Change from baseline in abdominal pain (AP) score by visit based on patient diary.
- Change from baseline in IBDQ total scores by visit.
- Change from baseline in IBDQ domain scores by visit.
- Change from baseline in hs-CRP by visit.
- Change from baseline in fecal calprotectin profile by visit.

Note: For the composite endpoints such as deep remission, please refer to Appendix 12.9 for detailed analysis convention.

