7.3 Previous Treatment and Concomitant Medications

The number and percent of subjects who received concomitant medication listed below will be tabulated by the generic name assigned by the most current version of the World Health Organization (WHO) Drug Dictionary in alphabetical order for concomitant medications. The prior medication, which is defined as any medication taken prior to the first dose of current study drug, has been reported in the feeder Study M15-993 and will not be evaluated here. No statistical comparisons will be performed.

A concomitant medication is defined as any medication other than study drug and the rescue medication that (1) was started prior to the first dose of study drug and continued to be taken after the first dose of study drug or (2) was started after the first dose of study drug, but was not started after the last dose of study drug. The definition of a concomitant medication for each of IV period and SC period can be defined similarly using the first dose of study drug in that period and the last dose of study drug in that period. A particular medication will be classified as "prior" or "concomitant" or "both" according to the rules provided in [Table 7](#), where "FD" is the date of the first dose of study drug and "LD" is the date of last dose of study drug plus 140 days.

Table 7. Rules for Prior and Concomitant Medication Classification

Medication		Medication Stop Date					
Start Date	Ongoing?	Missing	< FD	= FD	(FD, LD)	= LD	> LD
Missing	YES	1, 2					
	NO/Missing	1, 2	1	1, 2	1, 2	1, 2	1, 2
< FD	YES	1, 2					
	NO/Missing		1	1, 2	1, 2	1, 2	1, 2
= FD	YES	2					
	NO/Missing			2	2	2	2
(FD, LD)	YES	2					
	NO/Missing				2	2	2
= LD	YES	2					
	NO/Missing					2	2
> LD	YES	3					
	NO/Missing						3

- 1 = Prior, 2 = Concomitant, 3 = Post-treatment.
- "FD" is the date of the first dose of study drug.
- "LD" is the date of last dose of study drug plus 140 days.

Concomitant medications at baseline of Study M15-989 include prior medications that have a start date before first dose of study drug of Study M15-989 and are ongoing or have a stop date after first dose of study drug of Study M15-989.

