9.0 Efficacy Analysis

9.1 General Considerations

There is no formal statistical hypothesis test planned. Descriptive analyses will be used to analyze the proportion of participants achieving the efficacy endpoints. The study is designed to gain extensive documentation of safety and efficacy.

9.1.1 Analysis of Efficacy Endpoints by Variable Type**9.1.2 Missing Data Imputation for Efficacy Endpoints**

Missing data imputation will be done only for categorical efficacy variables. For the analysis other than efficacy, no imputation will be done for missing values.

Non-Responder Imputation (NRI)

The NRI approach is used for binary efficacy variables. These variables can take values of 'Achieved' or 'Not Achieved' or may be missing for any reason including discontinuation from study. According to the NRI imputation approach, all missing values will be considered as 'Not Achieved.' If a subject has missing value for a specific visit, the data will be imputed using NRI only for the period which the visit belongs to.

Observed Case (OC)

Observed case analysis will be performed, i.e., missing values will not be imputed. An analysis using only the observed data will be performed as a sensitivity analysis for primary and secondary efficacy endpoints.

Imputation of Missing Dates

For baseline, efficacy, and safety parameters, if the day and/or month are missing, the following conventions will be used to impute the missing dates:

- 01 for missing start day
- End of month for missing end day
- January 1st for missing start month
- December 31st for missing end month

In case of partially missing AE start and stop dates, the dates will be imputed by comparing to first dose date of study medication so that the corresponding AEs will be made treatment-emergent whenever possible. If the start date of an AE is partially

missing and the month is the same as the start date of a new therapy, the AE will be made treatment emergent to the new therapy.

In case of missing or partially missing study drug dosing dates, the dates will not be imputed. Subjects will be treated as not receiving dose on that date.

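### A response regained after the permitted prednisone re-increase counts as achieved in both the NRI and the observed-case analysis, so the SAP cannot separate it from a maintained response

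*SAP*

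**What the plan says.** **Endpoints.** SAP 4.3.2 defines the secondary binary endpoints by scores, with no condition on other treatment. Two examples are "Clinical remission by visit defined as a CDAI < 150" and "Clinical response by visit, defined by either a CDAI < 150 or a CDAI reduction from baseline of at least 100 points".

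**Missing data.** SAP 9.1.2 has one rule that turns a binary value into a failure: "According to the NRI imputation approach, all missing values will be considered as 'Not Achieved". The companion OC analysis leaves values as recorded: "An analysis using only the observed data will be performed as a sensitivity analysis for primary and secondary efficacy endpoints". Under SAP 6.4 the visit windows drop no post-baseline value. SAP 6.2 and the window footnotes keep data up to 140 days after the last dose, or up to the first M16-000 dose if that is earlier. A further sentence, which counts subjects who discontinue as failures, appears only in the PRO-2 appendix (SAP 12.2).

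**Steroids.** Protocol 4.2.2.1 asks for a taper at first remission on study drug. If response is lost at two consecutive visits during the taper, "the dosage of prednisone may be increased back to the dosage used at study entry". Stopping study drug is not attached to this.

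**Reporting.** SAP 7.3 opens its definition with "A concomitant medication is defined as any medication other than study drug and the rescue medication that" and never says what the rescue medication is. SAP 7.3.1 tabulates Crohn's-specific drugs for the 90 days before baseline and at baseline only.

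**The concern.** Protocol 3.2 names two goals: long-term safety data and early evidence that clinical response lasts. For the second goal, a patient who stays in remission off steroids and a patient who relapses, has prednisone raised and recovers are different outcomes. The SAP gives them the same value at the later visit. There is no control arm to absorb the difference. The planned sensitivity analysis shares the gap, because OC differs from NRI only in its handling of missing values. A reader of the by-visit response and remission tables could therefore not tell how much of the durability was achieved without renewed steroid treatment.

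**Working it through.** The plan states no figure on this point, so there is none to reproduce. The check is a trace of the rules, then a scale for the effect.

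**1. Can response be lost without a mandatory stop?** Let B be the 1311.6 baseline CDAI.
- Loss of response during the taper (Protocol 4.2.2.1): CDAI has fallen by less than 100, so CDAI > B − 100, at two consecutive visits.
- Mandatory stop for lack of efficacy (Protocol 3.3.4.1): CDAI > B + 100, confirmed by endoscopy, with CDEIS above 4.
- Gap: (B + 100) − (B − 100) = 200 CDAI points. A patient in this band has lost response, may have prednisone raised, and is not required to stop study drug for lack of efficacy.

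**2. What value does the later visit get?** Suppose CDAI is below 150 at a visit after the increase.
- The value is observed, so the NRI rule does not act.
- OC uses it as recorded.
- The windows keep it.
- Result: *Achieved* for clinical remission, and hence for clinical response, in both analyses. The same logic applies to the PRO-2, CDEIS and IBDQ endpoints, which are also score-only.

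**3. Does another planned output show it?**
- The endpoint in SAP 4.3.3 that requires at least 90 days off corticosteroids is exploratory. It covers only subjects on steroids at baseline who also meet the symptom and SES-CD entry cut-offs, and it uses stool frequency and abdominal pain rather than CDAI or CDEIS.
- SAP 7.3 counts subjects by generic drug name. A dose increase of a drug already being taken leaves no trace in such a table.
- SAP 7.3.1 stops at baseline.

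**4. How open is the route through other Crohn's drugs?**
- Against it: Protocol 4.2.1 limits concomitant therapy to essential care outside the gut. Protocol 3.3.4.1 stops study drug when a patient with lack of efficacy needs alternative therapy. Protocol 4.2.2.1 bars monoclonal antibodies and anti-TNF agents during treatment.
- Still open: values after study drug is stopped but within 140 days of the last dose; protocol deviations; and oral 5-ASA and Crohn's antibiotics, whose rows in the 4.2.2.1 table cover only the time before Visit 2.

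**5. Scale.** Planned N is about 60 (Protocol 3.1). If m patients at a visit are counted as successes only after intensified treatment, the shift is 100 × m / 60 points.

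| m (assumed) | Shift (points) | A rate of 70% (42/60, illustrative) becomes |
|---|---|---|
| 1 | 1.7 | 68.3% (41/60) |
| 3 | 5 | 65% (39/60) |
| 6 | 10 | 60% (36/60) |
| 12 | 20 | 50% (30/60) |

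The documents give no value for m.

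**The case against.** Using observed values whatever the co-medication is a legitimate treatment-policy description. Efficacy here is descriptive, with no hypothesis test and no primary efficacy analysis, and the main objective is safety. The re-increase only restores the entry dose. It is tied to the taper, and at the fastest permitted rate a 20 mg dose is tapered in 20 / 2.5 = 8 weeks, about one visit interval in the s.c. period. The two visits with lost response are themselves in the by-visit tables, normally as failures. A rule that fails every later visit for good would also penalise a patient who was briefly back on the entry dose and then steroid-free for years.

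Most of this stands. It limits how often the event can occur, and it is why the present count should be kept and the new rule needs a stated end. It does not remove the gap: the taper rate is a maximum, so tapers may last longer; the SAP does not label its count as treatment-policy; and a by-visit proportion cannot show that the same patient failed and then recovered on more steroid.

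Some stronger readings are tempting but not supported:
- *Nothing except a missing value is ever failed.* SAP 12.2 also fails discontinued subjects and gives clinical remission as an example, though its scope is unclear.
- *Oral steroids are unrestricted after Visit 2.* Protocol 5.1.2 asks for a stable dose until remission, and 4.2.2.1 then requires the taper.
- *Crohn's drugs may be freely added as treatment of an adverse event.* This joins "In case of adverse events in need of treatment, symptomatic therapy according to the judgment of the investigator will be permitted" to the instruction to record "Worsening of the underlying disease or of other pre-existing conditions" as an adverse event. The link is an inference, and the opening of Protocol 4.2.1 points the other way.
- *SAP 7.3 hides Crohn's drugs.* Its rescue medication is undefined; nothing shows that steroids, 5-ASA or antibiotics fall under it.

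**Conclusion.** The point holds for steroid re-increase: under the written rules, a response or remission restored that way is *Achieved* in both NRI and OC, and no planned output separates it from a maintained one. For other added Crohn's drugs it holds only through the narrower openings in step 4 of the working.

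The supplementary count can only equal or fall below the present one. By how much is unknown: 1.7 points per affected patient at N = 60 is arithmetic, while any number of patients is an assumption. A reader might go on to infer an overstatement of a particular size that grows over about four years of treatment. The documents do not support that. They give neither the share of patients on steroids nor a relapse rate, and the permission is tied to the taper rather than to time on study.

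What is affected is the interpretation of durability. No type I error, power or safety conclusion is involved. The change is worth making because it is cheap and serves a goal the protocol itself states.

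**What to change.** 1. **SAP 9.1.2 and 9.3.** Keep the current NRI and OC counts. For the secondary binary endpoints, add a pre-specified supplementary analysis beside them. It sets a visit to *Not Achieved* if, after the first M15-989 dose, systemic corticosteroid for Crohn's disease was started or increased, or another Crohn's-specific drug was started or increased. State whether the flag ends once the added treatment has been withdrawn for a set time, for example the 90 days already used in SAP 4.3.3.
2. **SAP 12.2.** State whether the discontinuation sentence applies to all binary endpoints, and how it fits with the use of data up to 140 days after the last dose.
3. **SAP 7.3.** Define the rescue medication or delete the term.
4. **SAP 7.3.1.** Tabulate Crohn's-specific drugs started or increased on study, by period.

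**Cost.** SAP wording, one derived flag and one added table. Corticosteroid changes already go on the Crohn's-specific co-medication eCRF page (Protocol 5.1.2), and concomitant and rescue therapies are also recorded (Protocol 4.2.1). The supplementary rates will be somewhat lower if such events occur. This is an analysis rule only and changes no clinical management.

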9.1.3 Dose Response Model and Dose Selection (if applicable)

Not applicable.

9.2 Primary Efficacy Analysis

There are no primary analyses for efficacy.

9.3 Secondary Efficacy Analyses

Secondary efficacy endpoints will be summarized descriptively by visit. They will be tabulated and descriptive statistics will be provided. Both Observed Case (OC) and Non-responder imputation (NRI) method will be used in the analysis.

9.4 Other Efficacy Analysis

There are no other efficacy analyses.

9.5 Efficacy Subgroup Analysis

The exploratory efficacy endpoints will be summarized descriptively by visit in the subgroup indicated. They will be tabulated and descriptive statistics will be provided. Both Observed Case (OC) and Non-responder imputation (NRI) method will be used in the analysis.

10.0 Safety Analysis

10.1 General Considerations

Safety analyses will include reporting of adverse events, laboratory, and vital signs measurements. All safety analyses will be performed on the safety analysis set.

The following summary statistics will be presented for subjects who have both baseline and post-baseline values for laboratory parameters and vital signs: the mean value at baseline and at each respective protocol specified visit, and the mean, standard deviation and median for changes from baseline. Categorical data will be summarized using frequencies and percentages.

10.2 Analysis of Adverse Events

10.2.1 Treatment-Emergent Adverse Events

Treatment emergent AEs (TEAEs) are defined as events that begin or worsen either on or after the first dose of the study drug in the current study and within 140 days after the last dose administration of the study drug in the current study for subjects not rolling over into Study M16-000 Sub-Study 3 or until the first dose of the study drug of Study M16-000 sub-Study 3 if the subject is enrolled into Study M16-000 Sub-Study 3.

Events where the onset date is the same as the study drug start date are assumed to be treatment-emergent, unless the study drug start time and the adverse event start time are collected and the adverse event start time is prior to the study drug start time. If an incomplete onset date was collected for an adverse event, the event will be assumed to be treatment-emergent unless there is other evidence that confirms that the event was not treatment-emergent (e.g., the event end date was prior to the study drug start date).

All analyses of AEs will be based on the number of patients with AEs (not the number of AEs).

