5.2.2.2 Adverse event and serious adverse event reporting

AE Collection

The Investigator shall maintain and keep detailed records of all AEs in their patient files.

The following must be collected and documented on the appropriate CRF(s) / eCRF by the Investigator:

- From signing the informed consent onwards through the Residual Effect Period (REP), until individual patient's end of trial: all AEs (serious and non-serious) and all AESIs.

The residual effect period (REP) for BI 655066/ABBV-066 (risankizumab) is defined as 20 weeks after the last trial medication application. Therefore, all AEs which occurred through the treatment phase and throughout the REP will be considered as on treatment (see [Section 7.3.3](#)). Events which occurred after the REP will be considered as post treatment events.

AE reporting to sponsor and timelines

In the event of an SAE, whether associated with study drug or not, the Investigator will notify Clinical Pharmacovigilance within 24 hours the site being made aware of the SAE by entering the SAE data into the electronic data capture (EDC) system. SAEs that occur prior to the site having access to the RAVE system, or if RAVE is not operable, should be documented on the SAE Non-CRF forms and emailed (preferable route) or faxed to Clinical Pharmacovigilance within 24 hours of the site being made aware of the SAE.

Email: [contact]
FAX to: [contact]

Risankizumab
1311.20/M15-989 Protocol Amendment 4
EudraCT 2015-001834-15

For safety concerns, contact the Immunology Safety Team at:

[figure not shown]
Immunology Safety Team

[name]
[name]

For any subject safety concerns, please contact the physician listed below:

Primary Therapeutic Area Medical Director:

In emergency situations involving study subjects when the primary Therapeutic Area Medical Director is not available by phone, please contact the 24-hour AbbVie Medical Escalation Hotline where your call will be re-directed to a designated backup AbbVie Therapeutic Area Medical Director:

Phone: 

AbbVie will be responsible for Suspected Unexpected Serious Adverse Reactions (SUSAR) reporting for the Investigational Medicinal Product (IMP) in accordance with global and local guidelines and Appendix A of the Investigator Brochure which will serve as the Reference Safety Information (RSI). The RSI in effect at the start of a DSUR reporting period serves as the RSI during the reporting period. For follow up reports, the

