7.3.3 Safety analyses

Since the main objective of this study is long term safety, the primary focus would be on incidence of drug-related AE and serious infection.

Adverse events will be coded using the Medical Dictionary for Regulatory Activities (MedDRA) coding dictionary. Summary tables and listings will be produced. All adverse events with an onset between start of treatment and end of the residual effect period (REP), a period of 20 weeks after the last dose of trial medication, will be assigned to the treatment period for evaluation.

All treated patients will be included in the safety analysis.

Statistical analysis and reporting of adverse events will concentrate on treatment-emergent adverse events. To this end, all adverse events occurring between start of treatment and end of the residual effect period will be considered 'treatment-emergent'. Adverse events that start before first drug intake and deteriorate under treatment will also be considered as 'treatment-emergent'. Frequency, severity, and causal relationship of adverse events will be tabulated by system organ class and preferred term after coding according to the current version of the Medical Dictionary for Drug Regulatory Activities (MedDRA). Safety analyses will focus on adverse events related to early discontinuation, immune suppression and injection site effects.

Laboratory data will be analysed both quantitatively as well as qualitatively. The latter will be done via comparison of laboratory data to their reference ranges. Values outside the reference range as well as values defined as clinically relevant will be highlighted in the listings. Treatment groups will be compared descriptively with regard to distribution parameters as well as with regard to frequency and percentage of patients with abnormal values or clinically relevant abnormal values. Analysis of laboratory measures will focus on haemotologic measures of immune suppression.

Vital signs, physical examinations, or other safety-relevant data observed at screening, baseline, during the course of the trial and at the end-of-trial evaluation will be assessed with regard to possible changes compared to findings before start of treatment.

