6.2 Definition of Final Observation

The final observation for each patient will be defined as the last non-missing post-baseline value collected no more than 140 days after the last dose of the study drug in Study M15-989. Any data collected beyond 140 days after the last dose of study drug in Study M15-989 will not be used for analysis but will be displayed in the data listings.

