10.2.1.7 Adverse Events by 100 Patient Years

TEAEs will be summarized by event rate per 100 patient years, defined as

$$100 \times \frac{\text{Number of TEAEs}}{\text{Total Patient Years}}$$

where total patient years is defined as below.

- Total patient years of SC period is defined as (min (the last risankizumab SC dose date in Study M15-989 + 140 days, the first dose date of risankizumab in Study M16-000 sub-Study 3) - the first dose date of risankizumab SC in Study M15-989)/365.25.
- Total patient years of IV period is defined as (min (the last risankizumab IV dose date + 140 days, the first dose date of risankizumab SC) - the first dose date of risankizumab IV in Study M15-989)/365.25.
- Total patient years of "all risankizumab" is defined as (min (the last risankizumab dose date in Study M15-989 + 140 days, the first dose date of risankizumab in Study M16-000 sub-Study 3) - the first dose date of risankizumab in Study M15-989)/365.25.

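### SAP 10.2.1 sets no 140-day cap on the treatment-emergent window for patients who enrol in M16-000, unlike the SAP's own patient-years, SAP 6.2 and the protocol; a minor inconsistency to reconcile

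*SAP*

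**What the plan says.** SAP 10.2.1 has two branches for the end of the treatment-emergent window. Patients who do not continue are covered "within 140 days after the last dose administration of the study drug in the current study for subjects not rolling over". Patients who continue are covered "until the first dose of the study drug of Study M16-000 sub-Study 3 if the subject is enrolled into Study M16-000 Sub-Study 3". The second branch has no 140-day limit and no earlier-of wording. Enrolment triggers it and dosing closes it.

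SAP 10.2.1.7 then uses these events as a numerator: "TEAEs will be summarized by event rate per 100 patient years". For all risankizumab, the patient-years stop at the earlier of "the last risankizumab dose date in Study M15-989 + 140 days, the first dose date of risankizumab in Study M16-000 sub-Study 3". The SC-period patient-years follow the same rule. So do footnote b of Tables 1 to 5 in SAP 6.4 and the SC-period concomitant-medication window in SAP 7.3.

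The protocol makes no exception for roll-overs. Section 7.3.3 says that events with onset from start of treatment to the end of the residual effect period, "a period of 20 weeks after the last dose of trial medication, will be assigned to the treatment period for evaluation". Section 5.2.2.2 adds: "Events which occurred after the REP will be considered as post treatment events".

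SAP 6.2 defines the final observation as "the last non-missing post-baseline value collected no more than 140 days after the last dose of the study drug in Study M15-989". Its second sentence is broader: data collected later than that are to be listed but not used for analysis.

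**The concern.** The numerator and denominator of an event rate should cover the same days. For a roll-over patient whose first M16-000 dose comes more than 140 days after the last M15-989 dose, SAP 10.2.1 keeps the event window open after SAP 10.2.1.7 has stopped counting time. An event in that stretch would be treatment-emergent under SAP 10.2.1, post-treatment under the protocol, excluded from analysis if SAP 6.2 is applied to it, and without person-time in the rate. The tables of patients with events would be affected too, because a late event could move a patient into the treatment-emergent count.

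Long-term safety is the primary objective, and Amendment 4 offers continuing patients a move to M16-000, so the roll-over branch will be used. Two programmers, one following 10.2.1 and one following 6.2, could produce different tables from the same data.

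**Working it through.** **The plan's own figure.** The residual effect period is 20 weeks in Protocol 5.2.2.2 and 7.3.3, and 20 × 7 = 140 days. The SAP's 140 days therefore agrees with the protocol; only the roll-over branch departs from it.

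**Inputs for one roll-over patient**
- T = days from first to last M15-989 dose. I use 1400 (nominal week 200, day 1401, in SAP Table 1), with 728 and 365 as assumed shorter courses.
- G = days from last M15-989 dose to first M16-000 dose. The documents do not give it, so the values are assumed.
- N = 60, the planned number of patients.

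**Formulas**
- Event window, SAP 10.2.1: T + G
- Patient-time, SAP 10.2.1.7: T + min(G, 140)
- Uncovered days: max(0, G − 140)
- Rate inflation under a constant event rate: (T + G) / (T + min(G, 140))

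**Per patient**

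| G (days) | Uncovered days | Inflation, T = 365 | T = 728 | T = 1400 |
|---|---|---|---|---|
| 56 | 0 | 1.000 | 1.000 | 1.000 |
| 140 | 0 | 1.000 | 1.000 | 1.000 |
| 168 | 28 | 1.055 | 1.032 | 1.018 |
| 196 | 56 | 1.111 | 1.065 | 1.036 |
| 252 | 112 | 1.222 | 1.129 | 1.073 |
| 365 | 225 | 1.446 | 1.259 | 1.146 |

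Up to 140 days the two windows coincide and nothing is wrong.

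**Study level.** Assume 5 of 60 patients have G = 196 and the other 55 have a 56-day tail.
- Uncovered time: 5 × 56 / 365.25 = 0.77 patient-years.
- T = 1400: patient-time is 55 × 1456 + 5 × 1540 = 87,780 days (240.3 patient-years). Inflation is 88,060 / 87,780 = 1.003.
- T = 365: patient-time is 55 × 421 + 5 × 505 = 25,680 days (70.3 patient-years). Inflation is 25,960 / 25,680 = 1.011.

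With 20 such patients the uncovered time is 20 × 56 / 365.25 = 3.07 patient-years, and inflation is 1.013 (T = 1400) to 1.042 (T = 365).

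**One misclassified rare event.** It adds 1/60 = 1.7 percentage points to the proportion of patients affected. Taking 60 × 1456 / 365.25 = 239.2 patient-years, it adds 100 / 239.2 = 0.4 per 100 patient-years.

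**A patient who enrols but is never dosed.** The closing date in 10.2.1 does not exist. The only text that could supply one is the second sentence of SAP 6.2.

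**After the fix.** Both windows equal T + min(G, 140). Uncovered days are 0 and inflation is 1.000 for every G.

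**The case against.** The strongest reply is that the SAP already contains the limit. The second sentence of 6.2 is worded generally, and applied to adverse events it would yield the earlier-of rule and close the window for a patient never dosed in M16-000. A reader might infer from 10.2.1 that the window simply never closes for such a patient; given 6.2, that is too strong. But the sentence sits under the definition of the final observation, its reach to adverse events is arguable, and it does not amend 10.2.1. What remains is a contradiction to settle, not a demonstrated bias.

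Second, Protocol 5.2.2.2 plans adverse-event collection only through the 20-week residual effect period, so few events with later onset should reach the database. This stands, and it limits the effect without correcting the definition.

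Third, a gap above 140 days is hypothetical. Dosing is every 8 weeks, roll-over is offered after the end-of-trial visit to patients on treatment, and the rationale in Amendment 4 is continuation. A reader might infer that the defect reaches most patients because most may roll over. The documents do not support that: the branch may apply widely, but it misbehaves only beyond 140 days or where no M16-000 dose is given. They set no maximum gap either, and roll-over waits on approval of an M16-000 amendment.

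Two further readings should be set aside:
- For short gaps the protocol's 20 weeks runs past the first M16-000 dose, where the SAP stops. That is a different contrast. The SAP's numerator and denominator already agree there, stopping at the next study's first dose is a reasonable attribution choice, and the fix below leaves it unchanged.
- A reader might see the same mismatch between the IV and SC periods. SAP 5.2 defines the safety groups by period, and SAP 9.1.2 assigns partially dated events to the new therapy, so allocation by period is evidently intended. An explicit rule for fully dated events is missing, but that is a separate matter of detail.

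**Conclusion.** The point holds in limited form. The roll-over branch of SAP 10.2.1 is wrong as written, because it conflicts with the SAP's own denominator, with SAP 6.2 and with the protocol. The visit windows and the SC concomitant-medication window use the earlier-of rule, so the missing cap looks like a drafting omission.

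The expected effect on the overall rate is small, and zero if every roll-over patient is dosed in M16-000 within 140 days. The study-level figures rest on assumed gaps, 60 patients and a constant event rate. The practical exposure is a single rare event, such as a serious infection or malignancy, that would change category. The study is descriptive, so no test is affected. Severity is minor.

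**What to change.** In SAP 10.2.1, define the end of the treatment-emergent window for every patient as min(last M15-989 dose + 140 days, first M16-000 dose, if any). This is the rule already used for patient-years in 10.2.1.7. It gives an end date for a patient who enrols in M16-000 but is never dosed, and no event would be treatment-emergent beyond the protocol's 20 weeks. List later events as post-treatment.

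The cost is one clause of SAP text and one programming condition. A few late events, if any exist, would move from the treatment-emergent tables to a listing.
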